## **12.4 Reporting procedures**

This study will follow the HS-IRB reporting and submission timeframes:

<https://kb.wisc.edu/images/group78/18324/ReportingTimeframesJanuary2013.pdf>

**Reporting time frames are in the Attachment.**

This document will take priority for timeframes. The PI is responsible for reporting to the IRB, DMC, and NIH.

### **12.4.1 Adverse Event Reporting**

Adverse events must be reported once the participant undergoes any study procedures and adverse events must be reported during the entire active study period. The IRB, DMC, and NIH will receive notifications about AEs.

### **12.4.2 Serious adverse event reporting**

Any SAE (including death, irrespective of the cause) occurring during the study will be immediately reviewed by the PI/study physician(s). Only SAEs meeting the Health Sciences IRB's reporting requirements will be submitted for IRB review. These SAEs will be submitted within the timeframe that is required by the HS-IRB and will also be reported to the DMC within the same timeframe.

The DMC will review all SAEs, regardless of reporting requirements to the IRB, every 12 months or ad hoc depending on the clinical case at the discretion of the PI/study physician(s). Each SAE will be followed until it is resolved or can be explained satisfactorily.

### **12.4.3 Unanticipated problem reporting**

The site investigator will be responsible for creating and completing a UP report form. Incidents that meet the OHRP criteria for UPs will be reported promptly per the HS IRB timeline (See Attachment).

- All UPs should be reported to appropriate institutional officials as required by the HS-IRB, the NIH, DSMB, and OHRP upon receipt of the report of the problem from the investigator per the HS IRB policy:  
<https://kb.wisc.edu/images/group78/18324/ReportingTimeframesJanuary2013.pdf>

The UP report will include the following information:

- Protocol identifying information: protocol title and number, PI's name, and the IRB project number;
- A detailed description of the event, incident, experience, or outcome;
- An explanation of the basis for determining that the event, incident, experience, or outcome represents an UP;
- A description of any changes to the protocol or other corrective actions that have been taken or are proposed in response to the UP.

#### **12.4.4 Reporting of pregnancy**

Participants will also be immediately withdrawn from the study if they report being pregnant or planning to become pregnant. Study data acquired up to the withdrawal date will be analyzed. No additional routine pregnancy reporting is indicated for this study.

### **12.5 Study Halting Rules**

#### **12.5.1 Participant Stopping Rules**

Participants will be informed that they have the right to withdraw from the study at any time for any reason, without prejudice to their medical care. The investigator also has the right to withdraw participants from the study for any of the following reasons:

- If study intervention is discontinued due to AE
- Protocol violation
- Study terminated

Participants may be withdrawn at the discretion of the PI for safety reasons. Women that are currently pregnant or plan to become pregnant during enrollment screening will be excluded from study participation. If a participant becomes pregnant during the study, she will be excluded immediately from further participation in all study activities. Pregnancy testing is not part of the study protocol. Once enrolled in the study, individuals in either the usual care or intervention group who become ineligible during the study (e.g., self-report of pregnancy) will be informed that their participation has ended and will be provided the reason for ending their study participation.

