### **8.3 Exclusion Criteria**

#### Patient

- weight loss of at least 5 lbs in the month prior to screening
- currently enrolled or enrollment in previous 3 months in a clinical or research program focusing on lifestyle change that could affect weight
- current use of weight loss medications (prescription or over-the-counter)
- history of bariatric surgery or planning to have bariatric surgery in the study timeframe
- residing in a nursing home or receiving home health care
- impaired hearing
- significant dementia, drug or alcohol abuse, or unstable psychiatric illness (e.g., schizophrenia or psychosis)
- current treatment for cancer or being treated for cancer (beside skin cancer) in the last 6 months
- use of Insulin, Sulfonylureas, or Meglitinides for diabetes due to increased risk for hypoglycemia
- pregnant, breastfeeding or planning to become pregnant within the study timeframe
- diuretic medication doses higher than hydrochlorothiazide 25 mg daily, furosemide 40 mg daily, Torsemide 20 mg daily, Bumetanide 1 mg daily or any use of Metolazone). Use of potassium-sparing diuretics is acceptable.
- chronic or unstable illness that would limit ability to participate (e.g., recent hospitalization; unstable heart disease in the 6 months prior to screening)
  - having acute coronary syndrome (ACS) including STEMI (ST-elevation myocardial infarction), NSTEMI (non-ST elevation myocardial infarction) and unstable angina (UA)
  - recent or impending coronary revascularization [recent coronary bypass grafting (CABG) or percutaneous coronary intervention (PCI)]
  - unstable arrhythmia (e.g., hospitalized for unstable atrial fibrillation, supraventricular tachycardia, ventricular tachycardia, ventricular fibrillation and/or firing of implantable cardiac defibrillator [ICD])
  - recent acute congestive heart failure exacerbation [requiring increased doses of oral or intravenous (IV) diuretics or hospitalization]
  - patient may be rescreened after sixth months
  - chronic kidney disease at stage 4 or higher
- exertional chest pain, dizziness or lightheadedness
- pain or other condition that prohibits mild-moderate exercise
- history of ascites requiring paracentesis
- planning to relocate in the next 2.5 years

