To enhance recruitment, we will do the following: discuss the study directly with partners to address any questions/concerns; frame weight loss as a couples' issue in recruitment materials; emphasize potential benefits of the intervention and outcome assessments to partners; offer sessions at different times of day; and offer two sessions that address communication to couples in the patient-only arm following the 24-month assessment. If partners no longer wish to receive intervention, then we will retain patients in the intervention (intent-to-treat analyses). If patients no longer wish to receive the intervention, then partners will no longer receive the intervention either. In such cases, we will ask patients (and partners) to return for outcome assessments, as we have done in our previous trials. Other efforts to maximize retention for outcome assessments include: administer the ASA24 online; e-mail/text reminders one week prior to the beginning of each window; place telephone calls and mail letters if participants are non-responsive to electronic reminders; compensate patients and partners \$40 each for completed interim assessments; and increase payments for the final assessment (\$60 each), as we did in the

MAINTAIN trial. In the MAINTAIN trial, 85% of patients returned for final assessments; in the CouPLES trial, 88% of patients and 70% of spouses did.(42, 50)

No participant will be excluded on the basis of race or sex. There have been mixed findings regarding the moderating role of sex in couples-based weight loss interventions. Failure to balance arms with respect to sex could, therefore, affect outcomes. Sex is explicitly accounted for in the study design in that it is a stratification variable. This variable, along with the other stratification variables of patient BMI and partner BMI, will be included in the statistical models for the primary outcome of weight, secondary outcomes of diet and physical activity, and mediation analyses.

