### 8.8.2 When and How to Withdraw Participants

Participants will be educated on the consent form that they are able to withdraw at any time without adverse effects. Participants may withdraw by alerting study staff in person, by telephone, or by email. If participants withdraw from the study, then their status will be updated in the tracking database, and no further contact will be made. Participants may be withdrawn at the discretion of the PI for safety reasons (e.g., self-report of pregnancy) or because they cannot participate meaningfully in the intervention (e.g., cannot communicate well by telephone). These individuals will be informed by study staff in person or by telephone that their participation has ended and the reason for ending their study participation. Their status will then be updated in the tracking database, and no further contact will be made.

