### 8.8.3 Data Collection and Follow-up for Withdrawn Participants

If partners no longer wish to receive intervention, then we will retain patients in the intervention. If patients no longer wish to receive the intervention, then partners will no longer receive the intervention either. Regardless of whether partners or patients request not to receive further intervention, we will ask patients and partners to return for outcome assessments. Patients who attend the first group session (i.e., provide a baseline weight) will be considered randomized and will be analyzed according to intent-to-treat principles, regardless of further intervention adherence; these individuals will not be replaced if they drop out subsequent to the first session. Consented participants who do not attend the first session (i.e., do not provide a baseline weight measurement) will not be considered randomized and thus will be replaced.

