Patients and their partners will return for outcome assessment visits at month 6, 12, 18 and 24 (Table 2). These outcome assessment visits may occur remotely via a video conference if necessary due to public health safety measures. For the patients, at months 6, 12 and 18: weight, dietary intake, physical activity, transformation of motivation, couples' efficacy, outcome efficacy, use of communal coping, social support for diet and physical activity, brief pain inventory-short form and COVID-19 will be measured by using the previously described methods. Additionally, at months 6, 12, 18 and 24, patients will complete a weight loss methods survey to see if there are any other ways they attempted to lose weight other than being in the study. For the transformation of motivation, couples' efficacy, outcome efficacy, use of communal coping, social support for diet and physical activity, brief pain inventory-short form, weight loss methods, and COVID-19 surveys, these will be sent ahead of their visits as a REDCap link via text and/or e-mail. The surveys will be completed at the outcome assessment visit if patients and partners do not complete them ahead of time, on their own. At month 24: weight, surveys (weight loss methods and COVID-19), dietary intake and physical activity assessments will be obtained. For the partners, all of the same measurements will be obtained at the same time-points except for physical activity. All outcome assessment visits will be completed by the WREN Research Coordinators. If patients or partners are unable to attend an in-person outcome assessment visit due to illness or public health safety measures, then we will collect their self-reported weight photos via a DOS REDCap link.

At months 3, 9, 15 and 21, transformation of motivation, couples' efficacy, outcome efficacy, use of communal coping, social support for diet and physical activity, and COVID-19 will be measured for both patients and partners. Patients and partner will be sent the surveys as a REDCap link via text and/or e-mail.

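### Patients the PI withdraws for safety, or because they cannot take part meaningfully, get no further contact, so a measurable month-24 weight may go uncollected

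*Combined protocol and SAP*

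**What the plan says.** The primary outcome is patient weight at month 24 (Section 7.1.1). Section 8.8.3 commits to an intent-to-treat analysis of everyone who attends the first group session, whatever their later adherence. Section 8.7.5 pays more for the final visit because the primary outcome is collected there.

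Three sections govern what happens when someone stops early.

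- **Section 8.8.2, withdrawal by the PI.** The grounds are safety (pregnancy is the example) or "because they cannot participate meaningfully in the intervention (e.g., cannot communicate well by telephone"). The consequence: "Their status will then be updated in the tracking database, and no further contact will be made."
- **Section 8.8.3, stopping by choice.** "Regardless of whether partners or patients request not to receive further intervention, we will ask patients and partners to return for outcome assessments." Section 8.5.1 describes patients or partners who no longer want the intervention, and says: "In such cases, we will ask patients (and partners) to return for outcome assessments, as we have done in our previous trials."
- **Section 12.5.1, investigator's right.** "The investigator also has the right to withdraw participants from the study for any of the following reasons". The list is an AE that stops the intervention, a protocol violation, and termination of the study. The section does not mention outcome visits afterwards.

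Section 12.7 blinds only the outcome assessors. Section 12.3 says AEs are followed until adequately resolved.

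**The concern.** Stopping an intervention and stopping measurement are different decisions. For patients who choose to stop, the plan keeps them apart. For patients whom the PI withdraws, it merges them. The plan's own example shows the problem: a person who copes badly with telephone calls cannot use the maintenance calls well, but can still stand on a scale at month 24.

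Two things are at stake. First, a primary outcome that could be obtained may become missing because of the protocol itself. Second, the decision may be taken by staff who know the arm, for reasons (an AE, or distress as described in Section 5.4.3) that may be related to weight. The primary analysis assumes data missing at random (MAR). Multiple imputation and missing-not-at-random (MNAR) analyses are planned as sensitivity analyses (Section 11.2.2.1). These model a missing weight; they do not replace one that could have been measured.

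**Working it through.** **1. Who is asked back.**

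| Route out | Source | Outcome visits afterwards |
|---|---|---|
| Patient or partner chooses to stop the intervention | 8.8.3, 8.5.1 | Requested |
| PI withdraws: cannot take part meaningfully | 8.8.2 | None; contact ends |
| PI withdraws: safety | 8.8.2 | None; contact ends |
| Investigator withdraws: intervention stopped for an AE | 12.5.1 | Not stated; falls under 8.8.2 if treated as a safety reason |

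The operative sentences of 8.8.3 and 8.5.1 turn on the wish of the patient or partner. No visible text restores weight collection after a withdrawal by the PI. The AE row is an inference, because 8.8.2 does not name AEs.

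**2. The plan's own sample size (Section 10.1).** Inputs: difference 2.5 kg, SD 19.9 kg, correlation 0.96, 80% power, 5% type I error (two-sided assumed), group size 15, ICC 0.01, attrition 20%.

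- Two-sample comparison of final weights: 995 per arm.
- Times 2(1 − 0.96) = 0.08: 79.6; plus one = 80.6 per arm, or about 160 in total, as stated.
- Design effect 1 + 14 × 0.01 = 1.14; 160 × 1.14 = 182.4 (plan: 180).
- 182.4/0.8 = 228, and 180/0.8 = 225 (plan: 230).

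The chain reproduces to within 3%.

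**3. Power.** SD of change = 19.9 × √0.08 = 5.63 kg. With 20% attrition, 230 × 0.8 = 184 remain, or 92 per arm, giving SE = 5.63 × √(2 × 1.14/92) = 0.89 kg and power of 80.6% (normal approximation). If withdrawals by the PI fall within the allowance of 0.20 × 115 = 23 per arm, planned power is unaffected. If they come on top of it:

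| Extra loss beyond 20% | Power |
|---|---|
| 1 point | 80.1% |
| 2 points | 79.6% |
| 5 points | 78.0% |
| 10 points | 75.2% |

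**4. Scale of bias.** The documents give no rate of withdrawal by the PI and no weight difference for such patients, so this is illustration only. Let k be the net extra withdrawals in one arm, and d the amount by which their true month-24 weights differ from the MAR prediction. Assume d = 3 to 6 kg, in either direction. Shift in the arm difference = (k/115) × d.

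- k = 1: 3/115 to 6/115 = 0.03 to 0.05 kg.
- k = 5: 0.13 to 0.26 kg.
- To move the estimate by 10% of the target (0.25 kg): k = 0.25 × 115/6 to 0.25 × 115/3 = 4.8 to 9.6, or 4.2% to 8.3% of an arm.
- To move it by half an SE (0.443 kg): k = 8.5 to 17.0, or 7.4% to 14.8% of an arm.

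This formula describes a simple difference in month-24 means. The planned test is a linear time-by-arm coefficient from weights at months 0, 6, 12, 18 and 24 (Section 10.2), and weights recorded before withdrawal stay in that model. Treat the figures as orders of magnitude.

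**The case against.** **The affected group may be nearly empty.** Pregnancy is the only safety example in 8.8.2, and ending outcome weights there is defensible. Difficulty on the telephone is partly screened out: hearing impairment is an exclusion, and English and a personal smartphone are required (8.2, 8.3). The protocol calls the study minimal risk (Section 12). This stands, and it is why the point is minor. It does not change what 8.8.2 directs when such a case arises.

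**The AE route is weaker than the telephone case.** A reader might infer that every patient whose intervention is stopped for an AE loses the month-24 weight. The documents do not support that. Section 12.5.1 grants a right, not a duty; 8.8.2 does not mention AEs; and 12.3 requires AEs to be followed to resolution, which sits badly with a literal end to contact. AE follow-up does not secure a weight, though, so the route remains possible.

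**Section 8.8.3 might be read more widely.** Its heading covers withdrawn participants in general. But its sentence concerns requests to stop, and 8.8.2 gives an explicit contrary instruction for withdrawals by the PI.

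**The consent form, manual of procedures and attached SAP are not visible.** They may say more. The no-contact sentence would still stand in the protocol.

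**Two further readings are tempting but not supported.**

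- Section 12.5.1 says that people "who become ineligible during the study (e.g., self-report of pregnancy) will be informed that their participation has ended", and Section 8.3 excludes "current use of weight loss medications (prescription or over-the-counter"). A reader might infer that a patient who starts such medication is dropped. The text does not say so, and Section 9.2.1 points the other way: "patients will complete a weight loss methods survey to see if there are any other ways they attempted to lose weight", at months 6 to 24.
- A reader might see protocol violation as a ground for withdrawal (12.5.1) as contradicting 13.4, which rules out exclusion for noncompliance. Violation is undefined in the visible text, and 13.4 concerns adherence to the behavioural intervention. Both can stand; at most this is a matter of wording.

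**Conclusion.** The point holds in limited form. As written, 8.8.2 ends contact with a randomised patient whom the PI withdraws for safety or for inability to take part meaningfully, and nothing visible brings that patient back to be weighed. An AE stop under 12.5.1 may fall under the same rule. Because the power is discretionary, the weight may be lost, not will be. Nothing here says that recorded data are discarded.

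Severity is minor. How many patients are affected cannot be derived from the documents. Under the assumed 3 to 6 kg departure, about 5 to 10 net withdrawals in one arm would be needed to move the month-24 difference by 10% of the target, and nothing in the documents suggests that such withdrawals are that common or that they differ by arm. A reader might infer that the primary comparison is materially biased; the documents do not support that. The case for change is that the gap serves no stated purpose outside pregnancy and safety, and costs little to close.

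**What to change.** **Section 8.8.2.** For withdrawals by the PI other than for pregnancy or planned pregnancy, keep the tracking-database update and replace the no-contact clause with wording such as: *The intervention will stop. The participant will still be asked for the remaining outcome weights (at minimum month 24, by visit or self-reported weight photo) and for any AE follow-up, unless he or she withdraws consent or the study physician judges that contact would be harmful.*

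**Section 12.5.1.** Reword the AE bullet so that it stops the intervention only, not study participation.

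**Section 9.2.1.** Extend the weight-photo route, now limited to illness or public health measures, to these participants.

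**Cost.** A wording amendment with IRB submission (Section 14), possibly a matching consent form change, and a home scale for anyone using the photo route. The month-24 visit and the photo route already exist. The sample size and analysis model do not change.

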#### **12.5.2 Study Stopping Rules**

This study may be temporarily suspended or prematurely terminated if there is sufficient reasonable cause. Written notification, documenting the reason for study suspension or termination, will be provided by the suspending or terminating party to investigator, funding agency and the regulatory authorities. If the study is prematurely terminated or suspended, the PI will promptly inform the IRB and DMC and will provide the reason(s) for the termination or suspension.

Circumstances that may warrant termination or suspension include, but are not limited to the following:

- Determination of unexpected, significant, or unacceptable risk to participants
- Insufficient compliance to protocol requirements
- Data that are not sufficiently complete and/or evaluable

### **12.6 Safety Oversight**

Independent safety oversight will be provided by The UW ICTR Data Monitoring Committee (DMC). The UW ICTR DMC is comprised of experienced members (core plus ad hoc) with expertise required to oversee this study. The DMC members will review protocol-specific reports created by statisticians using data pulled from DOS REDCap data management tool. These standard reports will include an overview of study objectives, a review of actual and projected accrual rates, an evaluation of patient demographics for balance of randomization, and a summary of the number and seriousness of adverse events. Source documents may be reviewed to allow the DMC to independently judge whether the overall integrity and conduct of the protocol remain acceptable based on data provided and reported by the PI. The DMC will make recommendations to the PI that could include actions of continuation, modification, suspension, or termination.

## **12.7 Unblinding Procedure**

Blinding of participants is not possible in behavioral interventions. Only WREN outcome assessors will be blinded.

# **13. Study Monitoring, Auditing, and Inspecting**

## **13.1 Medical Monitoring**

### **13.1.1 Study Monitoring Plan**

No independent study monitoring will be conducted.

## **13.2 Protocol Deviations**

A protocol deviation is any noncompliance with the clinical trial protocol, GCP, or MOP requirements. The noncompliance may be either on the part of the participant, the investigator, or the study site staff. As a result of deviations, corrective actions are to be developed by the site and implemented promptly.

The site PI/staff will be responsible for continuous vigilance to identify and report deviations to the protocol. These will be reported per the HS IRB requirements (see attachment). All deviations must be addressed in study source documents, reported to NIH Program Official, DMC, and IRB. Protocol deviations will be sent to the local IRB per their guidelines. The site PI/study staff is responsible for knowing and adhering to their IRB requirements.

